8.1.2 Laboratory Evaluations

Venipuncture schedule and blood volumes are shown in [Section 1.2](#) and [Appendix B, Table 3](#), respectively.

- **Clinical Laboratory Assessments: (Hematology, Coagulation, Chemistry and Urinalysis):** Blood and urine samples for clinical laboratory tests will be collected at the Screening Visit and on Check-in (Day -1) to determine eligibility.

Participants must be fasting at least for 4h before any blood draw for clinical laboratory assessments. These tests will include:

- Hematology (HEM): Complete Blood Count with absolute differential cell count (CBC w/Diff). The panel will include total white blood cell count (WBC), absolute count for neutrophils, lymphocytes, monocytes, basophils, and eosinophils, red blood cell count (RBC), platelet count, and hemoglobin.
- Coagulation (COAG): INR with prothrombin time (PT), activated partial thromboplastin time APTT).
- Chemistries (CHEM): Albumin, blood urea nitrogen (BUN), calcium, phosphorous (inorganic), creatinine, estimated glomerular filtration rate (eGFR) calculated by the CKD-EPI formula, electrolytes (sodium, potassium, chloride, total carbon dioxide [CO2]), magnesium, glucose (fasting), total bilirubin, direct bilirubin, alanine aminotransferase (ALT), aspartate aminotransferase (AST), alkaline phosphatase

(ALP), total protein, amylase, and lipase.

- Urinalysis (UA): Routine dipstick testing of clean-catch urine for occult blood, protein, glucose, nitrite, bilirubin, specific gravity, and pH.
 - If urine dipstick is abnormal for blood, protein, glucose, and nitrites, urine microscopy will be performed (for WBC, RBC, bacteria, and other cell counts), and the results will supersede those of the dipstick UA.
 - UA can be deferred until after the end of menses.

Clinical laboratory tests at the Screening Visit and Check-in (Day -1) should be in the normal reference range with exceptions. (See [Section 5.2, Inclusion Criterion #4](#)). Laboratory normal reference ranges are those included in the current version of the Manual of Procedures (MOP).

Other Exceptions to screening laboratory tests' normal reference ranges are:

- a. Labs performed as part of a panel but not included among the listed tests are to be recorded in the source record. Examples include direct bilirubin, RBC, hematocrit, mean corpuscular volume (MCV), mean corpuscular hemoglobin (MCH), mean corpuscular hemoglobin concentration (MCHC), red cell distribution width (RDW), mean platelet volume (MPV), nucleated red blood cell count (NRBC CT), and % white blood cells types, which are included in a CBC with WBC differential, INR, and specific gravity and pH resulted by dipstick urinalysis (UA). If abnormal per the laboratory normal reference range, they are not exclusionary and are not to be graded per Toxicity table individually; however, the investigator would make a clinical decision about their clinical significance.
- b. Menstruating females with a positive dipstick UA or microscopic UA may be retested following cessation of menses. Gross blood in urine that is confirmed due to menses is not a TEAE (but is for all other reasons).

- **Viral Serology Testing:** HIV antibody test (HIV 1 & HIV 2), Hepatitis B surface Ag (HBsAg, Hepatitis C virus (HCV antibody, and SARS-CoV-2 molecular diagnostic test (Cue Care™ test) for COVID-19.

The HIV and hepatitis tests will be performed at the Screening Visit only and all results must be negative for study eligibility.

The SARS-CoV-2 test will be performed at Check-in Visit (Day -1), and the result must be negative for study eligibility.

- **Pregnancy Test (females of child-bearing potential only):** A *serum β -HCG pregnancy test* will be done at the Screening Visit and a *urine pregnancy test* will be done at Check-in (Day -1) within 24 hours before receiving the initial study product. The results must be negative for determining eligibility and dosing with study drug(s).

- **Serum follicle stimulating hormone (FSH):** The test will be performed to confirm post-menopausal status in female participants at the initial Screening Visit only.
- **Urine Drug Screen (UDS):** Urine drug screen to assess for illicit (non-medical) use of amphetamines, cocaine metabolites, barbiturates, benzodiazepines, opiates, cannabinoids, tricyclic antidepressants, and phencyclidine. Urine creatinine will be measured as part of the profile to assess quality of collected sample.

UDS will be performed at Screening Visit and on Day -1. Results must be negative for study eligibility. Participants using any of these substances for medical reasons will also be excluded.

- **Urine Alcohol Test:** The test will be performed at Screening and Check-in (Day -1). Results must be negative for study eligibility.
- **Urine Cotinine Test:** The test will be performed at Screening and Check-in (Day -1). A positive result at Screening in a participant without history of heavy consumption of nicotine products is acceptable. The result of test done at Check-in (Day -1) must be negative for study eligibility.

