- (f) Focused PE is a symptom directed PE performed as needed to assess new symptoms reported from the time of Admission on Day-1 to before the first dose, and after first dose on Day 1 to the end of the study to assess treatment-emergent AEs as needed, except on Day 9 when a complete PE is performed.
- (g) VS include blood pressure (BP), heart rate (HR), respiratory rate (RR) and temperature (T) and assessed resting supine at Screening, Day-1, within 30 min before and 2 h (\pm 10 min) after each dose on Days 1 to 7, and once daily in the morning on Day 8 and on Day 9, or ET (See [Section 8.1.1](#) and [Section 8.3.1](#). Orthostatic blood pressure and heart rate are also assessed in the standing position for 1 minute \pm 15 seconds and 3 minutes \pm 15 seconds. **NOTE: VS are taken before drawing blood for safety lab tests, plasma PK, and serum for future research if consented. Supine VS are taken before orthostatic BP and HR.**
- (h) Serum pregnancy test at Screening and Urine pregnancy test on Day-1 (See [Section 8.1.2](#)).
- (i) FSH to confirm menopause in women with amenorrhea of 12 or more months at Screening.
- (j) UDS screening for illicit drugs described in [Section 8.1.2](#) and urine alcohol test.
- (k) Urine cotinine test for nicotine use at Screening and Day-1.
- (l) HIV antibody (HIV 1 and HIV 2), Hepatitis B virus surface antigen (HBsAg) and Hepatitis C virus antibody (HCV) tests at Screening Visit (see [Section 8.1.2](#)).
- (m) SARS-CoV-2 (Covid-19) molecular diagnostic Cue Care™ test at Check-in Visit (Day-1) (see [Section 8.1.2](#)).
- (n) Clinical laboratory tests at Screening, Day-1, before the first (morning) dose on dosing Days 2, 4 and 6, and on Day 8, or ET. (See [Section 8.1.2](#) and [Section 8.3.2](#)).
- (o) UA by dipstick at Screening, Day-1, and on Days 4 and 8, or ET. If abnormal for blood, protein, glucose and nitrites, a microscopic UA will be done. The results of microscopic UA will supersede the results of dipstick UA. UA will be postponed in a menstruating female [Section 8.1.2](#) and [Section 8.3.2](#)).
- (p) 12-lead ECGs at Screening, Day-1, before the morning dose on Day 4 and at Day 8 (before the 12h PK timepoint after evening dose on Day 7), unscheduled as indicated or ET (See [Section 8.1.1](#) and [Section 8.3.1](#)).
- (q) Enrollment will occur on Day-1 after eligibility is confirmed. **NOTE: Randomization will occur before administration of the morning dose on Day 1.**

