5.1 Inclusion Criteria

In order to be eligible to participate in this study, an individual must meet all of the following criteria:

1. Provision of signed and dated informed consent form.
2. Able to understand and willing to be available for all study visits and comply with all study procedures including Lifestyle Considerations (see [Section 5.4](#)) throughout the study.
3. Male and Female individuals, age 18-65 inclusive at time of enrollment.

4. Good general health by medical history (MH), physical examination (PE), and vital signs (VS), clinical laboratory tests and ECG within normal reference range.¹
 - Note 1: Lab exceptions include: lab test values that are within Grade 1 range per the Toxicity Table ([Appendix A](#)) are acceptable if not considered to be clinically significant by the investigator (PI, sub-investigator, or authorized clinician), with the exception of liver function tests (LFT) (transaminases ALT, AST, alkaline phosphatase (AP), total and direct bilirubin, serum creatinine, estimated glomerular filtration rate (eGFR) per the CKD-EPI formula, and urine protein, which must be within the laboratory normal reference range.
 - Note 2: Screening laboratory values that fall outside the laboratory normal reference ranges and the ranges are not listed within the Toxicity Table ([Appendix A](#)) (e.g., decrease aPTT) that are deemed Not Clinically Significant by the PI will be acceptable.
5. Ability to take oral medication and be willing to adhere to the dosing regimen.
6. Women of childbearing potential¹ must have practiced or use true abstinence² or use at least one acceptable primary form of contraception³ for specified periods⁴ before, during and after dosing.
 - Note 1: Not of childbearing potential – post-menopausal females (defined as having a history of amenorrhea for at least one year) or a documented status as being surgically sterile (hysterectomy, bilateral oophorectomy, salpingectomy, tubal ligation, or Essure[®] placement with a history of documented radiological confirmation test at least 90 days after the procedure).
 - Note 2: True abstinence is 100% of the time without sexual intercourse (the male's penis enters the female's vagina). Periodic abstinence [e.g., calendar, ovulation, symptothermal, post-ovulation methods] and withdrawal are not acceptable methods of contraception.

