PR interval prolonged (msec)	211 – 250 msec	>250 msec	Type II 2 nd degree AV block OR Ventricular pause >3.0 msec	Urgent Intervention indicated

Urine Microscopy

Urine Microscopy	Grade 1	Grade 2	Grade 3	Grade 4
Nitrite (dipstick)	1+	2+	>2+	
White blood cells (WBC) per HPF	0 – 10	11 – 50	>50 or gross	Hospitalization of intervention

Urine Microscopy	Grade 1	Grade 2	Grade 3	Grade 4
Bacteria (microscopic)	Few	Moderate	Many	Hospitalization or intervention

Estimating Severity Grade for Parameters Not Identified in the Grading Table

The functional table below should be used to grade the severity of an AE that is not specifically identified in the grading table. In addition, all deaths related to an AE are to be classified as Grade 5.

PARAMETER	GRADE 1 MILD	GRADE 2 MODERATE	GRADE 3 SEVERE	GRADE 4 POTENTIALLY LIFE-THREATENING
Clinical adverse event NOT identified elsewhere in the grading table	Mild symptoms causing no or minimal interference with usual social & functional activities with intervention not indicated	Moderate symptoms causing greater than minimal interference with usual social & functional activities with intervention indicated	Severe symptoms causing inability to perform usual social & functional activities with intervention or hospitalization indicated	Potentially life-threatening symptoms causing inability to perform basic self-care functions with intervention indicated to prevent permanent impairment, persistent disability, or death

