#### 4.5.1. Safety Variables

Venipuncture schedule and blood volumes are shown in schedule of assessments ([Table 3](#)). The following safety endpoints will be assessed:

- Chemistry (CHEM), Hematology (HEM), Coagulation (COAG), and Urinalysis (UA) clinical laboratory result safety parameters will be collected at Screening, Day -1, and prior to the morning dose on Days 2, 4, and 6, and on Day 8 or at early termination.
  - CHEM parameters: Electrolytes (sodium, potassium, total carbon dioxide [CO2]), calcium, chloride, creatinine, blood urea nitrogen (BUN), fasting glucose, total protein, albumin, total bilirubin, alanine aminotransferase (ALT), aspartate aminotransferase (AST), alkaline phosphatase (ALP), amylase, lipase, magnesium, and inorganic phosphorus.
    - Note 1: Estimate glomerular flow rate (eGFR) and direct bilirubin will be collected but not graded.
  - HEM parameters: Hemoglobin, platelets, white blood cells (WBC), neutrophils, lymphocytes, monocytes, basophils, and eosinophils.
    - Note 1: Red blood cells (RBC) will be collected but not graded.
  - COAG parameters: Prothrombin time and activated partial thromboplastin time (aPTT).

- Note 1: Prothrombin time international normalized rate (PT INR) will be collected but not graded.
- UA parameters: Nitrite, urine protein, and urine glucose via dipstick.
  - Note 1: pH, specific gravity, bilirubin, and occult blood will be collected but not graded.
  - Note 2: If urine dipstick is abnormal for blood, protein, glucose, and nitrites, urine microscopy will be performed (for WBC, RBC, and bacteria), and the results will supersede those of the dipstick UA.
- Vital signs (VS) will be collected at Screening, Day -1, within 30 minutes before and 2 hours ( $\pm$  10 minutes) after each dose on Day 1 through Day 7, and the mornings of Days 8 and 9.
  - Supine VS parameters: Body temperature (oral), systolic blood pressure (SBP), diastolic BP (DBP), pulse, and respiratory rate.
    - Note 1: BP will be taken after at least 5 minutes of resting.
  - Orthostatic VS parameters: SBP, DBP, and pulse
    - Note 1: Orthostatic parameters will be measured 1 minute  $\pm$  15 seconds and 3 minutes  $\pm$  15 seconds after standing.
- Electrocardiogram (ECG) results will be collected at Screening, Day -1, and prior to the morning dose on Day 4, and Day 8 (before 12h PK timepoint after Day 7 evening dose) or at early termination.

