**Table 8: Laboratory Adverse Event Grading Scale (continued)**

Parameter	Grade 1/Mild	Grade 2/Moderate	Grade 3/Severe	Grade 4/ Potentially Life-Threatening
change from baseline				
Platelets decrease – $\times 10^3/\mu\text{L}$	125 – 140	100 – 124	25 – 99	< 25
Leukocytes (WBC) increase – $\times 10^3/\mu\text{L}$	10.80 – 15.00	15.01 – 20.00	20.01 – 25.00	> 25.00
Leukocytes (WBC) decrease – $\times 10^3/\mu\text{L}$	2.50 – 3.50	1.50 – 2.49	1.00 – 1.49	< 1.00
Lymphocytes decrease – $\times 10^3/\mu\text{L}$	0.75 – 1.00	0.50 – 0.74	0.25 – 0.49	< 0.25
Monocytes increase – $\times 10^3/\mu\text{L}$	1.01 – 2.00	2.01 – 3.00	> 3.00	Intervention indicated
Basophils increase – $\times 10^3/\mu\text{L}$	0.16 – 0.50	0.51 – 0.80	> 0.80	Intervention indicated
Eosinophils increase – $\times 10^3/\mu\text{L}$	0.65 – 1.50	1.51 – 5.00	> 5.0	Hyper-eosinophilic
Neutrophils decrease – $\times 10^3/\mu\text{L}$	1.50 – 2.00	1.00 – 1.49	0.50 – 0.99	< 0.50
Coagulation				
Prothrombin Time – sec	11.2 – 12.3	12.4 – 13.4	13.5 – 14.0	> 14.0
Activated Partial Thromboplastin Time (aPTT) – sec	35.0 – 42.0	42.1 – 49.0	49.1 – 52.5	> 52.5
Urine Dipstick				
Nitrite	1+	2+	>2+	--
Urine Protein	Trace	1+	2+	Hospitalization or dialysis
Urine Glucose	Trace	1+	2+	Hospitalization for hyperglycemia
Urine Microscopy				
White blood cells (WBC) per HPF	0 – 10	11 – 50	> 50 or gross	Hospitalization or intervention
Red blood cells (RBC) per HPF	1 – 10	11 – 50	> 50 or gross	Hospitalization or packed red blood cells (PRBC) transfusion
Bacteria (microscopic)	Few	Moderate	Many	Hospitalization or intervention

 Liver function tests (LFT) include ALT and AST. Urine microscopy was only performed if urine dipstick was abnormal for blood, protein, glucose, and nitrites. The results of the urine microscopy would supersede the results of the urine dipstick.

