#### 14.3.5.3 Urinalysis Results

##### Table 36: Urinalysis Laboratory Results by Parameter, Maximum Severity, Time Point, and Treatment Group, Safety Population

[Implementation Note: This table will be a similar format to [Table 33](#). Urinalysis will be presented for Days -1 (baseline), 4, and 8 and for each treatment group. Headers will not be split into Low and High, e.g., “Mild/Grade 1”.

Parameters will be shown in the following order: Any Urinalysis Parameter, Bilirubin, Nitrite, Urine Protein, Urine Glucose, White Blood Cell Count, Red Blood Cell Count, and Bacteria.

Urine microscopy parameters (WBC Count, RBC Count, and Bacteria) were only collected conditionally and thus will only be included if at least 5 participants reported a graded event. Otherwise refer to [Table 32](#).]

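### Urine microscopy supersedes the dipstick with no limit by analyte, so the operative grade for urine protein and glucose is undefined; separately, the urine white-cell scale grades a zero count as mild

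*Protocol*

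**What the plan says.** **The replacement rule.** Protocol 8.1.2 sets the trigger as "If urine dipstick is abnormal for blood, protein, glucose, and nitrites", and continues: "urine microscopy will be performed (for WBC, RBC, bacteria, and other cell counts), and the results will supersede those of the dipstick UA". Footnote (o) of the protocol's Schedule of Assessments repeats it: "The results of microscopic UA will supersede the results of dipstick UA". SAP 4.5.1 (Note 2 under urinalysis) and SAP Table 2 footnote (o) carry the same rule, and SAP Table 8 footnote 2 adds: "The results of the urine microscopy would supersede the results of the urine dipstick". None of these five places restricts the rule to analytes that both methods report.

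**What each method measures.** Microscopy gives white cells, red cells and bacteria, plus other cells in the protocol only. The graded dipstick tests are in SAP 4.5.1: "UA parameters: Nitrite, urine protein, and urine glucose via dipstick". Dipstick occult blood is collected but not graded. In SAP Table 8, protein and glucose at trace, 1+ and 2+ are Grades 1, 2 and 3.

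**The white-cell scale.** The row "White blood cells (WBC) per HPF" has 0 – 10 as Grade 1 in both Protocol Appendix A and SAP Table 8, where Grade 1 is labelled mild. The red-cell row next to it in SAP Table 8 starts at 1.

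**Where the grades go.** SAP Table 14 counts participants who reach Grade 3 on a safety laboratory test. SAP Table 36 tabulates urinalysis by grade, with rows for nitrite, protein and glucose as well as the microscopy parameters. Listing 16 shows all urinalysis results with a column for the method.

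**The concern.** A replacement rule makes sense when the second test measures the same thing better. Microscopic red cells can stand in for dipstick occult blood. Nothing in a sediment can stand in for protein or glucose. If the rule is applied to the dipstick as a whole, the abnormal protein or glucose that helped to trigger microscopy stops being the result of record, and no protein or glucose result takes its place.

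Laboratory TEAEs and the number of participants with Grade 3 laboratory results belong to the primary safety and tolerability endpoints (Protocol section 3, SAP section 3). Two programmers working from the same text could produce different Grade 3 counts, and the arms are small enough for one participant to show.

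The white-cell bound is a separate fault that acts in the opposite direction: it produces a mild abnormality from a normal sediment.

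**Working it through.** The plan states no figure to reproduce here. The check applies the printed grades.

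**Inputs**
- Protein and glucose, dipstick: trace = 1, 1+ = 2, 2+ = 3 (SAP Table 8).
- Urine white cells per HPF: 0 – 10 = 1, 11 – 50 = 2, above 50 = 3 (Appendix A, SAP Table 8).
- Urine red cells per HPF: 1 – 10 = 1, 11 – 50 = 2, above 50 = 3 (SAP Table 8).
- Planned cohort: 8 active, 4 placebo (Protocol 4.1, SAP section 5). SAP Table 4 prints 6 for the 400 mg group, which does not agree with SAP section 5; 8 is used here.
- Four replacement participants, arms not stated (SAP 6.2), all included in the Safety Population once dosed (SAP 6.3.3).

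**Step 1: zero cells.** White cells = 0 falls in 0 – 10, so Grade 1. The lowest grade that any white-cell count can receive is 1. Red cells = 0 falls below 1, so ungraded. With a white-cell lower bound of 1, as for red cells, a zero count would also be ungraded.

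**Step 2: trigger read as any one abnormality.** Dipstick protein 2+, everything else negative; microscopy with no white cells, red cells or bacteria.
- Whole dipstick superseded: max(white cells 1, red cells 0, bacteria 0) = Grade 1, and that 1 comes only from the zero white-cell count.
- Analyte by analyte: max(protein 3, white cells 1, red cells 0, bacteria 0) = Grade 3.

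**Step 3: trigger read as all four abnormal.** An isolated protein 2+ never reaches microscopy and keeps Grade 3. Now take protein 2+ (3), glucose trace (1), nitrite 1+ (1) and occult blood abnormal (ungraded), with red and white cells each between 1 and 10 per HPF (1 and 1) and few bacteria (1).
- Whole dipstick superseded: max(1, 1, 1) = Grade 1.
- Analyte by analyte: protein stands, maximum = Grade 3.

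The gap between the readings is therefore present whichever way the trigger is taken. The trigger changes only how many participants are exposed to it.

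**Step 4: effect of one participant on an arm percentage**
- Active, 8: 1/8 = 12.5 points.
- Active, 8 + 4 = 12 if every replacement was active: 1/12 = 8.3 points.
- Placebo, 4 as planned: 1/4 = 25 points.

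**The case against.** The strongest reply is that the rule is loosely worded and the rest of the SAP shows what was meant. Table 36 keeps rows for protein and glucose, Table 8 grades them, and Table 14 counts anyone who reached Grade 3 without excluding superseded values. Protocol 8.3.3 treats abnormal post-treatment laboratory values as AEs. All of this fits replacement by analyte. It is good evidence of intent, but it sits against five unqualified statements, and no sentence says which value is analysed.

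Several stronger readings are tempting, and the documents do not support them.

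- *A Grade 3 proteinuria is erased.* No. Listing 16 retains both results by method. What is undefined is the operative grade, not the raw value.
- *The plan definitely reports it as Grade 1.* No. That follows only if the whole dipstick is superseded, and the isolated-protein example also needs the trigger's *and* to mean *or*.
- *The superseding microscopy result will usually go untabulated.* The Table 36 note says microscopy rows "thus will only be included if at least 5 participants reported a graded event", but it then sends the reader to Table 32, which lists abnormal urinalysis results. Because every microscopy is graded at least 1, the condition is met once five participants have one. It is a display choice that leaves the protein and glucose rows untouched.
- *The rule lets an abnormal protein through screening.* Inclusion criterion 4 names liver tests, renal measures "and urine protein, which must be within the laboratory normal reference range". Only the dipstick supplies a protein value, so microscopy cannot satisfy that requirement. Enrolment has also ended after Cohort 1 (SAP 2.1).
- *Every microscopy creates an AE.* The Table 33 note, whose format Table 36 follows, makes a graded result an AE only if severity worsened from baseline. Microscopy is conditional, so a participant may have none at baseline, and the documents do not say how worsening is then judged. A Grade 1 white-cell result cannot enter the Grade 3 count in any case.

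**Conclusion.** Two rules are wrong as written. The replacement rule covers analytes that microscopy does not measure, which leaves the analysed grade for urine protein and glucose open between two readings. The white-cell scale has no ungraded value, so a normal sediment is mild by definition.

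The reach is limited to urinalysis grading, but it touches the Grade 3 laboratory count and the laboratory TEAEs in the primary endpoints. For one participant with protein or glucose at 2+ and at most Grade 1 on microscopy, the maximum urinalysis grade is 3 or 1 depending on the reading. In the active arm that is 12.5 points with 8 participants, or as low as 8.3 if all four replacements were active. These sizes are illustrative: they assume a single affected participant who has no other Grade 3 laboratory result, and the documents give no rate at which it would happen.

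**What to change.** Add an SAP addendum, which SAP section 15 allows before final data lock, with two items.

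1. **Replacement rule.** State that dipstick protein and glucose grades stand and are the values used in Tables 14 and 36 and in TEAE grading. State that microscopy supersedes only what it measures, for example red cells for occult blood. Say explicitly how nitrite is handled when bacteria are reported. State whether the trigger's *and* means any or all of the four abnormalities, matching how the site applied it.
2. **White-cell scale.** Correct the Grade 1 lower bound in Table 8 so that a zero or normal count is ungraded. Starting at 1 would match the red-cell row; starting above the laboratory's normal limit is the alternative, but that limit is in the Manual of Procedures and cannot be checked here. Record the change as a departure from Protocol Appendix A.

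The five-participant condition in Table 36 and inclusion criterion 4 can stay as they are. The cost is a few lines of text and a small change to the grading program. No new data are needed, because both results are already listed by method.
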